8.7.2 Further Safety Assessments

8.7.2.1 Physical Examination

Complete physical examinations will be conducted according to the Schedule of Events (see Appendix 1). Any clinically significant change from baseline that results in a change in subject management will be considered an AE.

Physical examination will be performed for the following body systems:

- General appearance
- Skin/dermatological
- Eyes, ears, nose, throat
- Head and neck (including thyroid)
- Lungs
- Heart
- Abdomen (liver, kidney, spleen, gastrointestinal)
- Lymph nodes

- Musculoskeletal
- Nervous System

8.7.2.2 Vital Signs

Vital signs comprise the measurement of systolic and diastolic blood pressure, body temperature, respiration, and heart rate. All vital signs will be measured after the subject should be resting quietly for 1 minute. Heart rate should be measured immediately before or immediately after blood pressure measurement.

Vital signs will be measured at screening, baseline (before investigational product injection), 10, 30, 60 minutes post injection (Day 1), and at the 4- to 14-day follow-up visit.

Any clinically significant change from baseline that results in a change in subject management will be considered an AE.

8.7.2.3 Electrocardiogram

A standard 12-lead ECG will be obtained at screening and on Day 1 at least 10 minutes after Lymphoseek injection. The ECG will be measured with the subject in a resting position for at least 1 minute. No continuous ECG monitoring will be required.

On-site investigator's responsibilities

The immediate cardiac safety of the subject will be ensured by the on-site qualified physician. Any 12-lead ECG intervals, waveform abnormalities, and rhythm changes that are clinically significant in that they result in a change in subject management will be considered an AE. In the case of an SAE, once SAE notification is decided upon, investigators are required to follow the procedure described for SAE notification and document abnormal ECG findings (intervals and waveforms). Any interval data or abnormal waveform finding that resulted in an AE (i.e., change of patient management) must be followed for the duration of the subject's participation in the study until normalization or return to baseline takes place.

Each 12-lead ECG tracing must be signed and dated and stored in the subject's source documentation.

8.8 Other Procedures and Variables

8.8.1 Blood Sampling

8.8.2 Laboratory Data Related to Screening and Safety

Clinical laboratory tests to be evaluated in this study include hematology, serum chemistry, and urinalysis. Blood and urine samples for safety will be obtained according to the Schedule of Events (Appendix 1) and in accordance with NIH blood volume limits. Table 10 shows the parameters to be assessed:

Hematology	Hemoglobin (Hb), hematocrit (HCT), mean corpuscular volume (MCV), mean corpuscular hemoglobin (MCH), mean corpuscular hemoglobin concentration (MCHC), platelets, neutrophils, eosinophils, basophils, lymphocytes, monocytes, red blood cells (RBC), RBC Morphology, white blood cells (WBC)
Serum chemistry	Aspartate aminotransferase (AST), alanine aminotransferase (ALT), gamma-glutamyl transferase (gamma-GT), alkaline phosphatase, total bilirubin, creatinine, chloride, potassium, sodium, total protein, albumin, globulin, Bicarbonate, blood urea nitrogen (BUN)
Urinalysis	Color, clarity, specific gravity, pH, bilirubin, glucose, ketones, leukocyte esterase, nitrites, protein, urobilinogen

Table 10.Minimum Clinical Laboratory Parameters

A central laboratory will be used for all blood and urine samples to be determined in this trial.

The central laboratory will provide the necessary kits to collect the blood and urine samples and will also provide appropriate information regarding shipping of the samples.

Care is to be taken not to potentially produce an erroneous value, e.g., by inappropriate use of the tourniquet or forceful withdrawal of blood. Each original laboratory report will be retained in the subject's files.

All laboratory reports must be promptly reviewed by the investigator, and upon review, initialed and dated by the investigator. Change(s) in post-dose test values considered clinically significant, which would require either additional control or therapy and, in case of disturbing or influencing factor(s) on values/samples, details of the appropriate value(s) and the source of disturbance or influence (e.g., quality of sample, co-medication, etc.) are to be recorded. Good clinical practice would suggest that a copy of the safety laboratory results be available to the subject and to the subject's referring physician.

The following are general guidelines and are provided in order to assist the investigator in evaluating changes in laboratory values after the administration of investigational product. Since from previous clinical experience, these changes are unexpected, in all instances laboratory error must be considered and ruled out. One common cause of error is dilution of the blood sample, which occurs when blood is drawn through a fluid-filled catheter.

Changes in most individual laboratory values cannot be interpreted without concomitant/concordant changes in related parameters. For example, a decrease in hematocrit of approximately 5 percentage points (49% to 44%) at 24 hours post injection can be considered clinically significant, but without a similar change in hemoglobin and red blood cells (RBC), laboratory error must be ruled out. Shifts in hematocrit may also occur with changes in subject's hydration status. With comparable decreases in hematocrit, hemoglobin and RBC, the investigator must evaluate the subject for blood loss/hemorrhage, especially at

the site of venipuncture. If coagulopathy or hemolysis is suspected, appropriate follow-up, including diagnostic tests and treatment, should be undertaken. Decreases in platelet count by greater than 30% of baseline value or an absolute value of less than 50,000/ μ L after a normal baseline value should also be followed up to rule out laboratory error or an underlying problem, such as a coagulopathy.

Increases in 2 or more liver function and related parameters (alkaline phosphatase, AST, ALT, and bilirubin) that result in values twice that of the upper limit of the normal range must be followed up to rule out any acute liver and/or cardiac illness. The investigator must obtain the appropriate tests as indicated by the subject's clinical status. Changes in sodium, potassium and chloride that are greater than 20% of baseline value must be followed up.

In all instances of changes in multiple parameters, regardless of the magnitude, the investigator must evaluate the subject in light of the clinical signs and symptoms and institute appropriate treatment. There may be other abnormal laboratory changes not specifically noted above that the investigator may want to follow up as appropriate for a particular subject.

Any change in laboratory value which results in a change in subject management (additional controls or treatment required) will be reported as a clinically significant change. Clinically significant changes in laboratory parameters which are not the result of laboratory error are to be recorded as AEs.

Any clinically significant changes in laboratory values are to be followed up with repeated tests at appropriate intervals (as determined by the investigator and the medical monitor) until the values return to baseline level or until the abnormality is explained by the investigator. Such additional tests should also be done at the central laboratory and will be entered into the database.

The amount of blood to be withdrawn is shown in Table 11.

	Screening	After Surgery
Hematology	2 to 3 mL	2 to 3 mL
Chemistry	1 to 3 mL	1 to 3 mL
Total	3 to 6 mL	3 to 6 mL

Table 11.Amount of Blood Withdrawn

For subjects that weigh less than 2 kg, no more than 3 mL/kg of blood can be drawn at either time point. Blood and urine specimens will be sent to a central vendor for analysis. Specimen collection, packaging, and shipping instructions are provided in a separate laboratory manual.

9 STATISTICAL METHODS

9.1 Introduction

This study is a prospective, open-label study conducted at up to 10 study centers. The objectives of the statistical analyses are to establish the safety and diagnostic utility of Lymphoseek in targeting lymphoid tissue in pediatric patients with melanoma, rhabdomyosarcoma, or other solid tumors who are undergoing lymph node mapping.

A study center is defined as a treatment administration site or group of treatment administration sites under the control and supervision the same principal investigator.

9.2 Randomization Methods

There is no randomization planned for this study. All enrolled subjects will receive Lymphoseek, and Lymphazurin as an optional control agent if consistent with institutional practice.

9.3 Pooling of Study Centers

There will be no selective pooling of study centers. Subjects from all study centers will be pooled for the analysis.

9.4 Safety Variables

9.4.1 Primary Safety Variable

The primary safety variable is the incidence of adverse events.

9.4.2 Secondary Safety Variables

The secondary safety variables are the following:

- Vital signs (screening, at pre- and post-injection time points, and at the 4-to 14-day follow-up visit)
- Laboratory parameters (screening and after surgery)
- ECG parameters (screening and at the post-injection time point)

9.5 Pharmacokinetic Variables

Not applicable.

9.6 Diagnostic Variables

9.6.1 Primary Diagnostic Variables

The primary diagnostic variables for this study are:

- Subject localization rate (defined as the proportion of subjects with Lymphoseekidentified lymph nodes)
- Number of lymph nodes identified intraoperatively by Lymphoseek per subject
- Proportion of subjects who underwent preoperative SPECT or SPECT/CT
- Proportion of subjects with a lymph nodes identified preoperatively using SPECT or SPECT/CT
- Number of lymph nodes identified preoperatively using SPECT or SPECT/CT
- Agreement of the number of nodes identified by preoperative SPECT or SPECT/CT to intraoperative localization
- Subject and nodal agreement of central pathology assessment with local pathology assessment of the excised lymph node(s) to confirm the presence/absence of tumor metastases
- Nodal false negative rate for Lymphoseek-identified nodes (using blinded central pathology assessment and local pathology assessment)
- Nodal sensitivity for Lymphoseek-identified nodes (using blinded central pathology assessment and local pathology assessment)
- Upstaging (defined as the proportion of patients with pathology-positive lymph nodes who had at least one pathology-positive lymph node that was identified by Lymphoseek and had no other pathology-positive lymph nodes [i.e., identified by any other method])
- Change in subject nodal staging before and after surgery based upon Lymphoseekidentified nodes
- Changes in treatment plan and relation to lymph nodes identified by Lymphoseek

9.6.2 Secondary Diagnostic Variables

The secondary diagnostic variables for this study are for those subjects receiving both Lymphoseek and Lymphazurin:

- Subject localization rate for Lymphazurin
- Number of lymph nodes identified intraoperatively by Lymphazurin per subject
- Nodal concordance (defined as the proportion of lymph nodes identified intraoperatively by Lymphazurin that are also identified intraoperatively by Lymphoseek)
- Reverse nodal concordance (defined as the proportion of lymph nodes identified intraoperatively by Lymphoseek that are also identified intraoperatively by Lymphazurin)
- Subject concordance
- Subject reverse concordance
- Nodal false negative rate for Lymphazurin-identified nodes (using blinded central pathology assessment and local pathology assessment)
- Nodal sensitivity for Lymphazurin-identified nodes (using blinded central pathology assessment and local pathology assessment)

- Upstaging (defined as the proportion of patients with pathology-positive lymph nodes who had at least one pathology-positive lymph node that was identified by Lymphazurin and had no other pathology-positive lymph nodes (i.e., identified by any other method)
- Change in subject nodal staging before and after surgery based upon Lymphazurinidentified nodes

9.7 Sample Size Justification

Approximately 27 subjects will be enrolled into the study, at least 6 of whom have been diagnosed with melanoma and at least 6 of whom have been diagnosed with rhabdomyosarcoma. Enrollment will be open to up to 15 additional subjects with other tumor types in which ILM and sentinel lymph node biopsy (SLNB) are appropriate. At a minimum, 20 of the enrolled subjects will be ≤ 16 years of age and at least 25 subjects will complete the 4- to 14-day follow up. The sample size was chosen in order to provide a reasonable amount of data to assess the safety and diagnostic performance of Lymphoseek within this limited pediatric subject population.

9.8 Handling of Missing Data

There will be no missing value imputation used in this study. All endpoints will be analyzed with subjects who have non-missing data (i.e., a complete case analysis).

9.9 Statistical Analysis

9.9.1 Analysis Populations

The following analysis populations will be defined:

Safety: The safety population will include all enrolled subjects with administration of Lymphoseek.

Intent-to-treat (ITT): The ITT population will include all protocol-eligible subjects with administration of Lymphoseek (with or without Lymphazurin) and complete intraoperative lymphatic mapping.

Blue intent-to-treat (BITT): The BITT population will include all ITT subjects who were also administered Lymphazurin prior to ILM.

Per protocol (PP): The PP population will include all ITT subjects without major protocol violations.

All safety analyses will be conducted on the safety population. The analysis of the diagnostic endpoints will be conducted on ITT, BITT, and PP populations, as applicable.

9.9.2 Analysis of Baseline and Demographic Characteristics

Baseline and demographic characteristics will be summarized by tumor type and overall for all subjects in the safety population. Continuous variables will be displayed via summary statistics (mean, median, sample size, standard deviation, minimum, and maximum). Categorical variables will be summarized via counts and percentages.

9.9.3 Analysis of Primary Safety Variables

All AEs will be observed for each subject from enrollment until termination from the study. Prior to analysis, all AEs will be coded using MedDRA. Based on these coded terms, AEs will be summarized using system organ class and preferred term by tumor type and overall for all subjects in the safety population. AEs will also be summarized by severity, relationship to investigational product, and relationship to study procedure. All AEs will be listed.

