3.2 Justification for Study Design and Population

This study is designed to evaluate the use of Lymphoseek as an ILM and SLNB agent in pediatric subjects with melanoma, rhabdomyosarcoma, or other solid tumors for which ILM and SLNB is useful, and by determining the concordance of detection rates of Lymphoseek and of Lymphazurin in the subjects who have utilized both agents. In addition, for each agent used, the presence or absence of tumor in the nodes, the number of nodes detected per tumor type, and the change in patient staging will be determined.

As the primary objective of this study is the safety of Lymphoseek in this population, Lymphazurin is being used to the extent possible as an optional control in this study for ILM endpoints because it would not be feasible to evaluate Lymphoseek's performance relative to another gamma-emitting radiopharmaceutical (i.e., technetium sulfur colloid) in a withinsubject study design. A meaningful comparison of radiopharmaceuticals in a between-subject design would necessitate the enrollment of large numbers of subjects, which again would not be feasible, given the relatively small incidence of pediatric solid tumors for which ILM and SLNB is indicated. Additionally, the use of Lymphazurin is a concomitant procedure that provides real-time intraoperative assessment between Lymphoseek and Lymphazurin. Lastly, Lymphazurin is an appropriate comparator because lymphatic mapping with a VBD is recognized and authorized in the US and multiple EU countries as an experiential clinical practice agent, it has been a forming agent in the development of the theory/practice of SLNB, and, importantly, its use is supported by ASCO-SSO (Wong et al, 2012) and EANM-EORTC sentinel node guidelines in melanoma (Chakera et al, 2009). However, due to the potential for allergic reactions within this vulnerable population, the use of Lymphazurin is optional and should be used consistent with instutitional practice.

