5.4 Treatment Assignment

In this open-label, non-randomized study, all subjects will receive the same Lymphoseek treatment. The use of Lymphazurin is optional, consistent with institutional practice.

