8.4.2 Surgical Lymph Node Identification

- 1. If Lymphazurin is used, inject it into the dermis around the primary tumor site (see Lymphazurin insert for instructions) in accordance with institutional standards. No more than 3 mL will be injected.
- 2. Conduct an initial transcutaneous survey to identify the area of increased radioactivity that is separate from the injection site. The survey should include the entire lymph node (LN) basin(s) at risk.
- 3. Once an area of increased radioactivity is identified, an incision should be placed to make as direct an approach as possible to the LNs.
- 4. On entering the subcutaneous tissue, a blue lymphatic vessel or blue lymph node may be seen. If a blue lymphatic vessel is seen, carefully trace it proximally to a blue LN. In vivo counts should be recorded and LN removed.

OR

If no blue lymphatic vessel or blue lymph node is seen, or if Lymphazurin is not used, then using a combination of visualization and the handheld gamma detector, explore the lymphatic basin for the LNs. As dissection proceeds towards the LN, repeated use of the handheld gamma detector is helpful in maintaining a line of site to the lymph node. The count rate will increase as dissection approaches the Lymphoseek-containing lymph node(s).

- 5. Once an LN has been identified, in vivo counts should be taken prior to excision. In vivo counts will consist of a set of three 2-second counts or one 10-second count (depending on the device) over the lymph node. Determination of a positive finding (i.e., localization) is based on the in vivo definition above. Any LN count not meeting this threshold criterion will be considered a negative (non-localized) finding.
- 6. The method used to identify all LN(s) will be recorded (i.e., blue appearance, positive finding, or both) prior to excision.
- 7. To confirm the in vivo procedure, a set of three 2-second counts or one 10-second count will be recorded for the excised lymph nodes. The mean count of the ex vivo LN will be compared to the mean of normal tissue background counts, and the threshold criterion used to determine a positive finding for the in vivo LNs will be applied to the ex vivo specimens. The appearance and time of excision of the lymph node will be documented. Determination of a positive finding (i.e., localization) is

based on the ex vivo definition above. Ex vivo counts must be performed on all excised lymph nodes.

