8.7.1.2 Categories for Adverse Event Assessment

All AEs will be assessed and documented by the investigator according to the categories detailed below.

Seriousness

For each AE, the seriousness must be determined according to the criteria given in Section 8.7.1.5.

Severity

The intensity of an AE is classified according to the following categories, taking into account the possible range of the intensity of the event:

- Mild The adverse event is transient and easily tolerated by the subject.
- Moderate The adverse event causes the subject discomfort and interrupts the subject's usual activities
- Severe The adverse even causes considerable interference with the subject's usual activities and may be incapacitating or life-threatening.

Specific drug treatment

Any specific drug treatment will be documented.

Causal relationship to investigational product and/or Lymphazurin (VBD)

The investigator will use the following definitions to assess the relationship of the AE to the use of investigational product and/or Lymphazurin:

Event can be fully explained by administration of the **Definitely related:** investigational product and/or Lymphazurin. **Probably related:** Event is most likely to be explained by administration of the investigational product and/or Lymphazurin rather than the subject's clinical state or other agents/therapies. Event may be explained by administration of the investigational **Possibly related:** product and/or Lymphazurin or by the subject's clinical state or other agents/therapies. **Probably not related:** Event is most likely to be explained by the subject's clinical state or other agents/therapies, rather than the investigational product and/or Lymphazurin. Event can be fully explained by the subject's clinical state or other **Definitely not related:** agents/therapies.

For causality assessments, AEs meeting the categories of definitely, probably, or possibly related will be considered to be related to investigational product and/or Lymphazurin.

Causal relationship to study procedure

The investigator will use the following definitions to assess the relationship of the AE to the study procedure:

Definitely related:	Event can be fully explained by the study procedure.
Probably related:	Event is most likely to be explained by the study rather than the subject's clinical state or other agents/therapies.

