9.9.5 Analysis of Primary Diagnostic Variables

The localization rate, defined as the proportion of ITT subjects that had at least one lymph node identified intraoperatively, along with a 95% confidence interval will be computed for Lymphoseek for each tumor type and overall.

The average number of lymph nodes identified intraoperatively by Lymphoseek per subject, along with a 95% confidence interval, will be computed for each tumor type and overall.

The proportion of ITT subjects who had preoperative SPECT performed will be summarized by tumor type and overall. The proportion of patients who had a hot spot on the scan will also be summarized by tumor type and overall. For those patients with a hot spot, the time from Lymphoseek injection to hot spot localization will be summarized.

The average number of lymph nodes identified with preoperative SPECT per subject, along with a 95% confidence interval, will be computed for Lymphoseek by tumor type and overall.

The average difference in the number of lymph nodes identified with preoperative SPECT per subject and the number of lymph nodes identified intraoperatively per subject, along with a 95% confidence interval, will also be computed.

The nodal and subject agreement of central pathology assessment to local pathology assessment will be computed as follows:

	Lymph nodes whose local and central pathology assessments were either	
Nodal	both positive or both negative	
Agreement =	Lymph nodes with non-missing local and central pathology results	

Where agreement on the subject level means that a subject either has at least one pathologypositive node with local and central pathology or has all pathology-negative nodes with local and central pathology. For the analysis of nodal agreement and subject agreement, only nodes that have non-missing local and central pathology results will be considered. Along with the agreement proportions, a 95% confidence interval will be computed for each endpoint. Subgroup analyses by tumor type will also be performed within the ITT and PP analysis populations.

The nodal false negative rate will be computed for Lymphoseek as the number of pathologypositive lymph nodes that were missed intraoperatively by the tracer divided by the total number of pathology-positive lymph nodes. A 95% confidence interval will also be computed. False negative rates also will be calculated separately for the blinded central pathology assessment and the local pathology assessment.

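### AE incidence is tabulated only by tumor type and overall, so reactions to the optional blue dye cannot be told apart from Lymphoseek events

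*Combined protocol and SAP*

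**What the plan says.** Section 2.1 makes the safety and tolerability of Lymphoseek the primary objective, and Section 9.4.1 makes AE incidence the primary safety variable. On who is analysed, Section 9.9.1 says: "The safety population will include all enrolled subjects with administration of Lymphoseek". On the dye, Section 5.4 says: "The use of Lymphazurin is optional, consistent with institutional practice". Section 3.2 gives the reason: "due to the potential for allergic reactions within this vulnerable population, the use of Lymphazurin is optional". The safety population therefore holds children with and without dye.

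Section 9.9.3 plans two kinds of summary, plus a listing of every event. The first: "AEs will be summarized using system organ class and preferred term by tumor type and overall". The second: "AEs will also be summarized by severity, relationship to investigational product, and relationship to study procedure". Neither is by dye.

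On attribution, Section 8.7.1.2 asks the investigator to "assess the relationship of the AE to the use of investigational product and/or Lymphazurin", using one five-level scale. Section 8.7.1.3 then requires the relationship to the investigational product and to study conduct, with no separate entry for the dye.

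For the main diagnostic result, Section 9.9.5 has the ITT localization rate "along with a 95% confidence interval will be computed for Lymphoseek for each tumor type and overall". Section 9.9.1 defines ITT as including subjects whether or not they had dye.

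**The concern.** The trial is meant to describe the safety of Lymphoseek in children, but its headline safety figure is taken over two exposures. Lymphazurin is given within hours of Lymphoseek, and the protocol names it as a possible cause of allergic reactions. A dye reaction adds to the overall AE incidence exactly as a Lymphoseek reaction would. Because dye use follows the site, the reported incidence depends partly on which sites enroll.

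The usual safeguard would be the table of related events. Here it cannot be relied on, because the rating does not ask which of the two agents is suspected. Even with perfect ratings, the incidence of all AEs would still be shown without reference to dye.

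A smaller form of the same question arises for intraoperative localization, where the dye may help a surgeon reach a node that is then counted as hot.

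**Working it through.** **Inputs.** Planned enrollment is about 27 (Section 9.7). The documents do not give the share receiving dye (s) or the AE incidence with dye (p_dye) or without it (p_alone), so all three are assumptions shown as ranges. Section 9.9.3 plans no confidence interval for AE incidence. The exact two-sided 95% (Clopper-Pearson) intervals below only indicate size.

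**1. The plan's own figure.** 6 melanoma + 6 rhabdomyosarcoma + 15 other = 27, which agrees with Section 9.7. That section gives no precision target for AE incidence, so there is nothing further to reproduce.

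**2. What pooling reports.** Pooled incidence = p_alone + s × (p_dye − p_alone). Assume 5% without dye and 15% with dye:
- s = 25%: 5 + 0.25 × 10 = 7.5%
- s = 50%: 5 + 0.50 × 10 = 10.0%
- s = 75%: 5 + 0.75 × 10 = 12.5%

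The pooled figure equals the no-dye figure only if nobody receives dye or the dye adds no events.

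**3. An example in counts.** Assume 13 of 27 receive dye and two of them react.
- As planned: 2/27 = 7.4% (0.9% to 24.3%)
- With dye: 2/13 = 15.4% (1.9% to 45.4%)
- Without dye: 0/14 = 0% (upper limit 23.2%)

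**4. Precision without dye.** With no events in n children, the upper limit is 1 − 0.025^(1/n).

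| Assumed dye share | With dye | Without dye | Upper limit, 0 events without dye |
|---|---|---|---|
| 25% | 7 | 20 | 16.8% |
| 50% | 14 | 13 | 24.7% |
| 75% | 20 | 7 | 41.0% |

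For comparison, 0/27 has an upper limit of 12.8%. Read as a statement about Lymphoseek without dye, that would overstate what the data can exclude.

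**5. Can the planned tables recover the split?** Tumor type, severity and relationship to procedure carry no information on dye. The relationship table draws on a rating that covers either agent. The listing shows individual events but gives no incidence by dye. Section 9.9.1 defines BITT, a set of dye recipients, but assigns all safety analyses to the safety population.

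**6. Localization.** In Section 8.4.2, step 4 lets a blue vessel lead the surgeon to a node. Around it, for every subject, come a gamma survey of the whole basin (step 2), an incision placed on the area of raised radioactivity (step 3), counts before excision (step 5), a further survey of the remaining basin (step 8), and probing until selected node counts are negative (step 9). Section 8.4.1 calls a node hot by a count threshold specific to the tracer. For dye to raise the per-subject rate, it must lead to a hot node that all this would have missed, and that node must be the subject's only hot one.

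**The case against.** The strongest reply is that the objective concerns Lymphoseek in children undergoing mapping, with dye as optional standard care, so the pooled incidence describes the population actually treated. All AEs are listed with onset times, and Section 9.9.4 leaves room for more safety analyses in a separate statistical analysis plan. A split would also not isolate Lymphoseek: every child goes on to surgery, dye use follows site practice, and the strata are tiny. Even the assumed 2/13 against 0/14 gives a Fisher p-value of 78/351 = 0.22.

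Much of this stands. It means the split must be descriptive and is not a test. It does not remove the point, since a listing is not an incidence table and Section 9.9.4 names no analysis by dye.

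A reader might infer something stronger from step 4 of Section 8.4.2 ("If a blue lymphatic vessel is seen, carefully trace it proximally to a blue LN"): that the dye finds the nodes and Lymphoseek takes the credit, so localization is inflated as well. The documents do not support this. The gamma steps set out above apply to every subject, and step 6 records for each node whether it was found by color, by counts or by both. Section 9.9.1 also allows diagnostic endpoints to be run in BITT where applicable, so Lymphoseek results in dye recipients may be shown and the remainder found by subtraction. Preoperative imaging comes before the dye (Sections 7.2.7 and 8.3), so SPECT results are unaffected. The adult Phase 2 intraoperative rate in Section 1.2.2 is 96.2%. If children were similar without dye, guidance could add at most 100 − 96.2 = 3.8 points.

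**Conclusion.** The safety point holds. As written, AE incidence is a mixture over dye use, and neither the planned breakdowns nor the joint causality rating can separate dye reactions from Lymphoseek events. The size cannot be fixed from the documents. Under the assumed rates of 5% and 15%, the pooled incidence runs from 7.5% to 12.5% as the dye share goes from 25% to 75%. The dye shares, rates and event counts are all assumptions. If almost no child, or almost every child, receives dye, the mixing largely disappears, although in the latter case there would be little experience without dye.

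The localization point is secondary and minor. Inflation by dye guidance is possible but limited, and Section 9.9.5 is best read as leaving the split unspecified. Nor would a split by dye give a clean estimate of the safety of Lymphoseek alone, because site differences and operative events remain in both strata.

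**What to change.** In Section 9.9.3, add AE incidence by Lymphazurin received (yes/no) beside the overall column. Among recipients, show onset before and after the dye. AE onset date and time are already required by Section 8.7.1.3, so the only other item is the dye administration time, if the eCRF does not already hold it. Events before the dye cannot be due to it. Events after it will still mix dye, Lymphoseek and surgery, because the dye is given at or during the operation.

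State in the plan that the split is descriptive, non-randomized, confounded with site and based on small numbers, with no test between strata.

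As a minor addition to Section 9.9.5, show the intraoperative Lymphoseek localization rate and nodes per subject for ITT subjects with and without dye, next to the overall figure. SPECT results need no change.

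The cost is some table columns and at most one data field, with no extra subjects or procedures. The main risk is over-reading small strata, which the labelling addresses.
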